4 PLANNED ANALYSIS SCHEDULE

4.1 Interim Analyses

A number of interim analyses will be performed while data collection is ongoing. The planned analyses are outlined below, along with the estimated dates of completion. Since the study is an observational, noninterventional, single-arm study, no statistical adjustments will be made to the results of any of the interim or final analysis. The reporting of data in multiple phases while the study is still ongoing may be taken as an interim analysis in terms of procedural efforts needed to summarize these data, but it will not serve as a means to modify the study conduct.

4.1.1 Year 1 Analysis

Around the end of the first year of the study, descriptive analyses of questionnaire responses and Baseline patient characteristics will be performed using all available data. Interim analyses of all primary and secondary endpoints for patients who have completed the 6-month Follow-up will also be conducted. [REDACTED]

[REDACTED]

[REDACTED]

4.1.2 Baseline Analysis

After the last patient enrolled in the study completes a Baseline questionnaire [REDACTED] an analysis will be performed to summarize the burden of CS for all patients (n = 643) at the time that XERMELO was initiated as a new treatment. This analysis will include summaries of all questionnaire items as well as interim analyses of all primary and secondary endpoints for patients who have completed the 6-month Follow-up.

4.1.3 Year 2 (Primary Endpoint) Analysis

Around the time that the last patient enrolled in the study completes the initial 6-month Follow-up questionnaire, the analysis of endpoints associated with the primary study objective and all secondary study objectives will be conducted. All descriptive analyses conducted at Year 1 will also be repeated. Interim analyses of other study endpoints will be conducted for subgroups of patients having 12, 18, and 24 months of Follow-up data. [REDACTED]

[REDACTED]

[REDACTED]

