2.3 Study Endpoints

2.3.1 *Primary Endpoint*

The primary endpoint of the study is the proportion of patients with CS who are satisfied with their overall symptom control, 6 months after initiating treatment with telotristat ethyl (XERMELO).

2.3.2 *Secondary Endpoints*

The following secondary endpoints will be assessed 6 months after initiating treatment with telotristat ethyl (XERMELO):

- The proportion of patients reporting satisfaction of CS-related diarrhea control
- The proportion of patients reporting satisfaction of CS-related flushing control
- The proportion of patients reporting reduction in rescue SSA use
- The proportion of patients reporting reduction in the dose of long-acting SSA injection
- The proportion of patients reporting reduction in the frequency of long-acting SSA injection
- The proportion of patients reporting an overall improvement in CS control after initiating XERMELO based on PGIC

- The proportions of patients who had reduction in work-related absenteeism, presenteeism, activity impairment, and overall productivity loss after initiating XERMELO based on the WPAI-SHP
- The proportion of patients reporting weight gain

2.3.3 *Other Endpoints*

Other endpoints include incidence of CS-related hospitalizations, incidence of CS-related emergency room (ER) visits, and incidence of mortality at 6-month intervals for up to 3 years after initiation of treatment with XERMELO.

Another endpoint, not described in the protocol, is the proportion of patients with a reduction in the number of bowel movements. This endpoint will be assessed at the 6-month Follow-up after initiation of treatment with XERMELO.

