2.4 Sample Size Determination

The sample size was derived by satisfying design assumptions for the primary study endpoint of the proportion of patients with CS who are satisfied with their overall symptom control, 6 months after initiating treatment with telotristat ethyl (XERMELO). Of specific interest is the proportion of patients with CS who are at least somewhat satisfied with their control of CS at 6 months, defined as those patients with a response of either "very satisfied" or "somewhat satisfied". This proportion will be estimated as x/n , where x is the number of patients in the study who are either "Very satisfied" or "Somewhat satisfied", and n is the number of patients with a non-missing response for the primary endpoint. Two-sided 95% confidence limits (CLs) will be calculated for this proportion using normal approximation. The true proportion may be approximately 50%; hence, an expected proportion of 50% was used in the sample size calculation as it requires the largest n . It is desired for the proportion to be known with a precision, ω , of 5%, that is, for the CLs to be $(x/n) \pm \omega$. Based on the expected proportion of 50% and the precision requirement of 5%, $n = 385$ patients are needed to have a non-missing response for the primary endpoint. Assuming that 40% of the patients who participate in the study will drop out prior to the 6-month survey, then a minimum of $N = 643$ patients, with CS who initiate treatment with XERMELO, should be entered into the study.

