4.1.4 Year 3 Analysis

The same summary analyses performed at Year 1 will be performed around the time when the first enrolled patient completes 3 years of Follow-up. Interim analyses of other study

endpoints will be conducted for subgroups of patients having 12, 18, 24, and 30 months of Follow-up data. [REDACTED]
[REDACTED]

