5.1.5 Other Endpoint Analyses

5.1.5.1 Analyses of Incidence of Emergency Room Visits, Hospitalizations, and Mortality

Incidence proportions for patients with at least 1 ER visit, at least 1 hospitalization, and mortality during each 6-month Follow-up interval will be reported along with 95% CLs. The denominator for each incidence proportion will be the number of patients enrolled in the

study at the beginning of that particular 6-month interval who also provide a non-missing response to the questionnaire item for each type of event.

The time to the first occurrence of a CS-related ER visit, time to the first occurrence of a CS-related hospitalization, time to the first occurrence of a CS-related ER visit or hospitalization, and time to mortality will be analyzed using the nonparametric Turnbull estimation method ([Turnbull, 1976](#)) for interval-censored data available in SAS PROC ICLIFETEST for each 6-month interval during Follow-up. These tables will display the number of patients still at risk at the beginning of the interval along with the number of events and censored observations within each interval. Estimates of the survival probability (the proportion of patients without the event) will be provided for the upper boundary of each interval, and these probabilities will also be displayed as figures. Estimated quartiles for event-free time (with 95% CLs) will be reported.

If death dates are available for the analysis of mortality, this analysis will be performed using the Kaplan-Meier method instead of the Turnbull method. Estimated quartiles for survival time (with 95% CLs) will be reported, and estimated survival probabilities will be displayed as Kaplan-Meier curves.

Details for all ER visits and hospitalizations, including the reason for the visit or hospitalization, will be provided in data listings.

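### Read literally, SAP 4.1.3 and 4.1.4 limit the Year 2 and Year 3 interim mortality, hospitalization and ER analyses to patients alive, on XERMELO and responding at month 12, 18, 24 or 30

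*SAP*

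**What the plan says.** The interim populations are set in the schedule section of the SAP. For Year 2, SAP 4.1.3 says: "Interim analyses of other study endpoints will be conducted for subgroups of patients having 12, 18, and 24 months of Follow-up data". For Year 3, SAP 4.1.4 says that interim analyses of the other study "endpoints will be conducted for subgroups of patients having 12, 18, 24, and 30 months of Follow-up data".

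SAP 2.3.3 identifies these endpoints: "Other endpoints include incidence of CS-related hospitalizations, incidence of CS-related emergency room (ER) visits, and incidence of mortality at 6-month intervals". It also lists a bowel-movement endpoint, assessed only at month 6, which is not at issue here.

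The methods for these endpoints are in SAP 5.1.5.1. For the proportions, it counts the patients in this "study at the beginning of that particular 6-month interval who also provide a non-missing response to the questionnaire item for each type of event". For time to event it uses the Turnbull estimator, or Kaplan-Meier for mortality if death dates are available. The tables show patients at risk, events and censored observations per interval.

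Three other provisions matter:
- SAP 2.1 and 3.1 describe Follow-up as a web questionnaire every 6 months.
- SAP 3.2.7 and protocol 5.1.1 end participation when XERMELO is stopped. Protocol 6.3 withdraws a patient after one missed survey in a year.
- SAP 3.2.7 takes deaths from the specialty pharmacy, not from the survey.

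**The concern.** A patient who has month-L survey data must have been alive, still taking XERMELO and still answering at month L. A subgroup defined that way is selected on what happened after baseline, and death is one of the outcomes being measured. Deaths before month L cannot appear in it. Hospitalizations and ER visits already reported by patients who later died, stopped or were lost also disappear.

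The selection could be sizeable. SAP 2.4 plans on "Assuming that 40% of the patients who participate in the study will drop out prior to the 6-month survey". Protocol 3.2 records the sponsor's assumption that satisfied patients stay on treatment and have better long-term outcomes. If that is so, remaining in the subgroup is related to the outcome. At stake is whether the Year 2 and Year 3 reports describe the patients who started XERMELO or only those who remained.

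**Working it through.** **1. The plan's own figures.** The documents give no figure for the interim mortality or event analyses. The sample size in SAP 2.4 reproduces: n = 1.95996² × 0.5 × 0.5 / 0.05² = 384.15, rounded up to 385. Then 385 / (1 − 0.40) = 641.7, rounded up to 642, against a stated 643. The one-patient difference has no bearing on this point.

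**2. One patient under each rule.** Take a patient hospitalized at month 4 who reports it in the month-6 survey and dies at month 8.
- Under the time-to-event method in SAP 5.1.5.1, the hospitalization counts in the first interval and the death in the second.
- In a subgroup with month-12 survey data, the patient is absent and both events are lost.

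**3. Mortality up to month L.** Protocol 3.1 cites median survivals of 33 and 90 months for two u5-HIAA strata in a 76-patient midgut NET study. I assume exponential survival and, for illustration only, that these medians bracket this cohort. Deaths by month L are 1 − 0.5^(L/median).

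| L (months) | Median 90 | Median 33 | Subgroup with month-L data |
|---|---|---|---|
| 12 | 8.8% | 22.3% | 0% |
| 18 | 12.9% | 31.5% | 0% |
| 24 | 16.9% | 39.6% | 0% |
| 30 | 20.6% | 46.7% | 0% |

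For example, 1 − 0.5^(12/33) = 0.223 and 1 − 0.5^(24/90) = 0.169. A subgroup defined by enrolment at least L months before the cut gives the two middle columns.

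**4. Deaths after month L.** Pharmacy-reported deaths between month L and the data cut can still be counted. I assume uniform entry over the 18 months first planned in protocol section 6, with monthly hazard h = ln 2 / median. At a month-24 cut, patients in the 12-month subgroup have 0 to 12 further months, so later deaths are 1 − (1 − e^(−12h)) / (12h): 4.5% (median 90) and 11.6% (median 33). At a month-36 cut they have 6 to 24 further months, so later deaths are 1 − (e^(−6h) − e^(−24h)) / (18h): 10.8% and 26.6%.

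**5. Does the wording also fit elapsed time?** With the same uniform entry, the share of patients with enough calendar time is (cut − L) / 18, limited to between 0 and 1.
- Month-24 cut: 67% for 12 months, 33% for 18 months, about 0% for 24 months.
- Month-36 cut: 100%, 100%, 67% and 33% for 12, 18, 24 and 30 months.

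Staggered entry alone would therefore create subgroups with these labels.

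**6. Hospitalization and ER visits.** The documents give no event rates for leavers. The overall rate is (1 − s) × p(stay) + s × p(leave), where s is the share leaving. Assuming 15% in stayers, 30% to 45% in leavers and s of 20% to 40%, it runs from 0.8 × 0.15 + 0.2 × 0.30 = 18% to 0.6 × 0.15 + 0.4 × 0.45 = 27%, against 15% in the subgroup. If leavers and stayers have the same risk, there is no difference.

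**The case against.** The strongest reply is that the sentence concerns timing. Section 4 is a schedule, entry is staggered, and the subgroups may simply be patients enrolled long enough ago. Where the SAP means completers, in 4.1.1 and 4.1.2, it says so in different words. SAP 5.1.5.1 sets the estimators without a completer subgroup, and protocol 10.4.1 has no such restriction. The disposition table in SAP 5.1.3.1 would still show discontinuations with reasons. Deaths may arrive only as counts per interval, and such counts could not be restricted to survey completers.

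Much of this stands. The elapsed-time reading is possible, and text next to both sentences is redacted and might settle it. But the sentence selects on having data. Follow-up in this SAP means a survey, and nothing visible says whether 4.1.3 or 5.1.5.1 governs at interim. A programmer could follow the sentence as written. Section 5.1.5.1 is not a complete remedy either: its requirement of a questionnaire response, applied literally to mortality, drops patients who die before the survey.

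A reader might infer that interim mortality will be reported as 0% whatever the truth. The documents do not support that. It needs the literal reading, and even then zero applies only up to month L (step 4). A reader might also infer a definite understatement of hospitalization or ER incidence. The documents give no rates from which to derive one.

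**Conclusion.** Wrong as written, with limited reach. Taken literally, SAP 4.1.3 and 4.1.4 condition the interim estimates on survival, continued treatment and response up to month L, and so depart from the method in SAP 5.1.5.1. Under the assumed medians of 90 and 33 months, the deaths excluded are about 9% to 22% of patients by month 12 and 17% to 40% by month 24. The existence of the selection does not depend on those medians; its size does. The size of any hospitalization or ER bias is unknown and depends on whether leavers are at higher risk.

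It would go too far to extend this to the study's main results. The primary and secondary endpoints are month-6 proportions, and the final analysis in SAP 4.2 carries no such restriction. SAP 4.1 says the interims will not be used to change study conduct.

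**What to change.** 1. In SAP 4.1.3 and 4.1.4, define the subgroups by time from enrolment to the data cut (at least 12, 18, 24 or 30 months), whether or not the patient is still in follow-up.
2. State that the Turnbull or Kaplan-Meier estimates use all enrolled patients with censoring, and cross-refer to SAP 5.1.5.1.
3. In SAP 5.1.5.1, give the mortality proportion a denominator of patients enrolled at the start of the interval, with no requirement for a questionnaire response.
4. Label the hospitalization and ER proportions as applying to survey responders. Those events are patient-reported, so the limitation remains.

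The cost is a few sentences and no new data. The change removes the survivor selection from the time-to-event estimates. It does not remove the assumption that censored patients have the same risk as those who remain, and the interim report should say so.

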4.1.4 Year 3 Analysis

The same summary analyses performed at Year 1 will be performed around the time when the first enrolled patient completes 3 years of Follow-up. Interim analyses of other study

endpoints will be conducted for subgroups of patients having 12, 18, 24, and 30 months of Follow-up data. [REDACTED]
[REDACTED]

4.2 Final Analysis

When data collection is completed [REDACTED] the final analysis will be performed. This analysis will include all full questionnaire summaries for Baseline and each Follow-up, as well as all analyses that correspond to the exploratory objectives for the study. A dry run of the final analysis will be conducted prior to database lock using a preliminary cut of the study data, and the results from this dry run will be reviewed by RTI-HS and Lexicon before database lock.

After database lock, topline results for the remaining study objectives will be produced and provided to Lexicon for review. All remaining tables and figures for the final analysis will then be produced and provided to Lexicon for review prior to the preparation of the study report.

5 STATISTICAL ANALYSIS

5.1 Statistical Methods

5.1.1 General Considerations

Derivation of analytic variables will be detailed in a separate analytic variable specification document to be produced in Microsoft Excel. This document will be developed at the time of the first interim analysis and will be maintained through the final analysis. It will be provided to Lexicon at the end of the study, along with the corresponding SAS data sets.

All analyses will be descriptive in nature. For continuous and ordinal variables, the number of available observations, means, standard deviations (SDs), medians, minimums, and maximums will be provided. For categorical variables, the frequency and percentage in each category will be displayed. For computation of percentages, missing values and "Prefer not to answer" responses will not be included in the denominator. Results will be presented by study time point, where applicable. Additionally, all questionnaire data will be displayed in listings. Height and weight information will be collected in feet and inches and in pounds but will be summarized in the tables in centimeters and kilograms, respectively. By convention, dates will be displayed in DDMMYYYY format (eg, 17JAN2017). For the times since diagnosis of CS and diagnosis of primary NET and all time-to-event analyses, the date of Baseline questionnaire completion will be considered as Day 1, and times will be expressed in months or years, as appropriate. The day before the date of Baseline questionnaire completion will be considered Day -1; there will be no Day 0.

All analyses will be performed in SAS, Version 9.4 or higher (SAS Institute, Cary, NC).

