5.1 Overall Study Design

In this study, the 2 specialty pharmacies, tasked with distributing XERMELO to patients, will be responsible for the identification and recruitment of patients. All eligible patients initiating treatment with XERMELO will be invited to participate in this study.

Individuals assigned by the specialty pharmacies (the ‘site staff’) will be responsible for describing the study to patients. An initial verbal consent will be obtained to collect personal contact information and to share it with the [REDACTED] and/or Research Triangle Institute (RTI) (collectively, the ‘study team’) for the purpose of providing additional information about the study, collecting informed consent, and managing access and/or support for the web-based survey.

The specialty pharmacies will send contact information to the study team, for patients who express interest in participation, via an approved method of communication noting the patient's unique specialty pharmacy identification (ID) number, first name, phone number, electronic mail (e-mail) address, and preferred time of contact (eg, morning, mid-day, evening). For patients who do not provide consent for further contact, the specialty pharmacies will be asked to provide aggregate data to the study team including patient(s) age, sex, geographic region, insurance type, reason for refusal to participate, and total number of patients who refused to provide consent.

As this study will be completed via an online survey and patients are to complete the enrollment process independently, electronic consent will be utilized for this study. Enrollment will be self-directed through a unique survey link sent directly to the patient's e-mail address. Each patient receiving an invitation to the survey will be assigned a numerical patient ID code; the patient ID will be assigned by the study team, based on a subject ID log at each specialty pharmacy. If successful enrollment is not logged within 30 days of the initial survey e-mail invitation or within 14 days of the subsequent survey e-mail invitations, the study team will make up to 3 attempts to contact the patient via e-mail and/or telephone to complete the enrollment process for study participation. The enrollment process and Baseline survey may be completed anytime within the 30-day window, at a time convenient for the patient.

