8.3 Prescription Fill Data

Information regarding a patient's initial prescription fill and subsequent refill(s) will be collected.

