3 DATA SOURCES AND VARIABLES

3.1 Data Sources

Data will be collected from patients electronically using web-based questionnaires. Patients who enroll in the study will complete a Baseline questionnaire within 30 days of enrollment and up to 6 Follow-up questionnaires at 6-month intervals after Baseline.

Prescription fill data, type of insurance, and reasons for discontinuation, including mortality, will be collected directly from the specialty pharmacy using a process that is still being determined and will be described in a separate document.

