3.2.5 Work Productivity and Activity Impairment Questionnaire—Specific Health Problem (WPAI-SHP)

The WPAI-SHP is a self-administered questionnaire ([Reilly et al., 1993](#)) comprising 6 questions that measure the effect of health problems on participants' ability to work and participate in regular activities based on their experiences in the previous 7 days. This questionnaire will be administered at Baseline and at the initial 6-month Follow-up.

The WPAI-SHP includes 4 domains (absenteeism, presenteeism, work productivity loss, and activity impairment). All participants will be asked whether they are employed (Q1) and how their CS-related problems affected their regular activities (Q6). Employed participants will be asked about hours of work missed due to CS-related problems (Q2), hours of work missed for any reason (eg, vacation, holidays, time off to participate in this study) (Q3), hours actually worked (Q4), and the degree that CS affected their productivity while working (Q5). An integer scale from 0 to 10 is used for Q5 and Q6, where 0 corresponds to no effect and 10 corresponds to complete effect.

Responses to the items are scored to produce the following 4 domains:

- Absenteeism: work time missed due to CS = [REDACTED]
- Presenteeism: impairment while working due to CS = [REDACTED]

- Work productivity loss: overall work impairment due to CS = [REDACTED]
[REDACTED]
- Activity impairment: activity impairment due to CS = [REDACTED]

Each score is then multiplied by 100 to express domains in terms of impairment percentages, with higher numbers indicating greater impairment and less productivity (ie, worse outcomes).

3.2.6 *Carcinoid Syndrome-related Health Care Resource Utilization*

At Baseline and at each Follow-up, questionnaire items will ask patients about ER visits and hospitalizations during the prior 6-month period. Data collected will include the following:

- The number of ER visits and the CS-related reason for each visit
- The number of hospitalizations, the number of nights for each stay, and the CS-related reason for each hospitalization

3.2.7 *Study Discontinuation and Mortality*

Patients will be terminated from the study if they discontinue the use of XERMELO, withdraw consent for participation, or are lost to follow-up. Information on reasons for discontinuation will be provided by the specialty pharmacy.

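### Baseline is not tied to the start of XERMELO, so some Baseline WPAI-SHP scores may be on-treatment values, which would bias the four WPAI reduction endpoints toward no change

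*SAP*

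**What the plan says.** **Time as named.** SAP 2.3 places the primary and secondary endpoints 6 months after XERMELO is started. The other endpoints include "incidence of mortality at 6-month intervals for up to 3 years after initiation of treatment with XERMELO".

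**Time as measured.** SAP 5.1.1 says "the date of Baseline questionnaire completion will be considered as Day 1"; that rule covers times since diagnosis and the time-to-event analyses. SAP 3.1 adds "Patients who enroll in the study will complete a Baseline questionnaire within 30 days of enrollment", and then "up to 6 Follow-up questionnaires at 6-month intervals after Baseline". SAP 2.1 counts the same 30 days from the e-mail invitation, and Protocol 5.1 says "The enrollment process and Baseline survey may be completed anytime within the 30-day window". Protocol Appendix A labels Baseline as Day 1 with a tolerance of +30 days, and month 6 with ±14 days.

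**Use of Baseline.** Under SAP 3.2.5 patients answer the WPAI-SHP "based on their experiences in the previous 7 days", at Baseline and at month 6. SAP 5.1.4 takes reduction from Baseline in four domains as secondary endpoints and also summarizes the change scores. SAP 4.1.2 treats the Baseline data as the burden of disease when XERMELO was started.

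**Start date.** Protocol 8.3 says "Information regarding a patient's initial prescription fill and subsequent refill(s) will be collected". No visible passage uses the first fill to date Baseline or month 6.

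**The concern.** A change-from-Baseline endpoint needs a reference measured before treatment. Here recruitment runs through the pharmacies that dispense the drug, the Baseline survey has a 30-day window, and nothing visible orders the survey before the first dose. Protocol 5.1.1 has each survey confirm that treatment is ongoing, and Protocol 8.2.1.6 asks for the XERMELO regimen with hospital events collected from Baseline onward. Both fit a Baseline that can fall after dosing has begun.

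A Baseline WPAI completed a week or more after the first dose describes an entirely treated week. If treatment helps, part of the benefit is already in the reference value. The proportion with a reduction and the mean change then both shrink, and the Baseline burden summary looks milder than it was. Without the interval from first fill to Baseline, a reader of the results could not tell how far this had happened.

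**Working it through.** **1. The plan's own figure.** SAP 2.4 uses an expected proportion of 0.50, a half-width of 0.05 and two-sided 95% limits: n = 1.96² × 0.5 × 0.5 / 0.05² ≈ 384.2, rounded up to 385, as stated. With 40% dropout, 385 / 0.60 = 641.7, rounded up to 642 against the stated 643, a gap of one patient. The timing question does not touch the sample size.

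**2. Which endpoints use a pre-dose Baseline value.**

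| Endpoint | Reference | Exposed to an on-treatment Baseline? |
|---|---|---|
| Overall, diarrhea and flushing satisfaction | Month-6 rating alone | No |
| SSA changes (Protocol 8.2.1.2) | Since starting XERMELO | No |
| PGIC (Protocol 8.2.1.3) | Since starting XERMELO | No |
| Weight change (SAP 3.2.1) | Since starting XERMELO | No |
| Bowel movements (SAP 5.1.5.2) | Since starting XERMELO | No |
| Four WPAI-SHP domains (SAP 5.1.4) | Baseline score, 7-day recall | Yes |

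Baseline satisfaction is worded for the period before XERMELO (Protocol 5.1.1), so its wording protects it.

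**3. Share of Baseline WPAI recalls on treatment.** Inputs from the documents: a 30-day window and a 7-day recall. Assumptions: completion is uniform over days 0 to 30 from invitation, and the first dose is L days after invitation. L is not in the documents.

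- Fully on treatment (completed on day L + 7 or later): (23 − L) / 30
- Partly on treatment: 7 / 30
- Entirely before treatment: L / 30

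| L (days) | Fully on treatment | Partly | Before treatment |
|---|---|---|---|
| 0 | 23/30 = 77% | 23% | 0% |
| 7 | 16/30 = 53% | 23% | 23% |
| 14 | 9/30 = 30% | 23% | 47% |

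The fully treated share reaches zero at L = 23. Every recall is before treatment at L = 30.

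**4. Timing of the month-6 survey.** Take 6 months as 182.6 days, the survey window as ±14 days, and Baseline on day B after invitation, with B from 0 to 30. Days since first dose = B − L + 182.6 ± 14.

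- Anchored to first dose: 168.6 to 196.6 days (5.5 to 6.5 months).
- As planned, L = 0: 168.6 to 226.6 days (5.5 to 7.4 months).
- As planned, L = 14: 154.6 to 212.6 days (5.1 to 7.0 months).

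This reads month 6 as counted from actual Baseline completion. That is an inference from SAP 3.1 and Appendix A, but on no reading is month 6 counted from the first dose.

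**The case against.** **Eligibility limits the problem.** Prior exposure to XERMELO is an exclusion, enrollment takes place through the e-mailed link, and Protocol 5.1 puts enrollment and the Baseline survey in one window. A patient dosed on the invitation date would normally be exposed before enrolling. This makes the 77% case hard to sustain. It also means that each share above presupposes patients who enroll before the first dose and complete the survey later, or an exclusion read as exposure before the current prescription. It does not close the gap, because SAP 3.1 allows up to 30 days between enrollment and Baseline.

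**The Day 1 rule is narrow.** A reader might infer from SAP 5.1.1 that every endpoint has the wrong time origin. The documents do not support that: the rule covers only times since diagnosis and time-to-event analyses, and most survey endpoints need no Baseline value.

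**Starting event follow-up at Baseline is defensible.** A reader might also infer that hospitalizations between first dose and Baseline are lost. They are not: SAP 3.2.6 has the Baseline survey ask about the prior 6 months. Baseline completion is when patients come under observation, and it suits the 6-month recall intervals of the Turnbull analysis. Moving the origin to first fill with delayed entry would be a change of method, and may be unworkable if deaths arrive only as interval counts (SAP 3.2.7). What stands is a labeling mismatch with endpoints named by time since initiation.

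**The stakes are limited.** The analyses are descriptive, the bias would understate benefit, and three of the four WPAI domains apply only to employed patients. The separate variable specification and the pharmacy-data document were not available and might address the point.

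**Conclusion.** The point holds for the WPAI-SHP endpoints. Their Baseline reference may be an on-treatment value for some patients, and the bias is toward no change if treatment improves WPAI. The share is unknown: about 30% to 53% of recalls are fully on treatment for a first dose 14 to 7 days after invitation, under uniform completion, and fewer if dosing starts later. The 77% figure is an upper case and should not be read as an estimate. The effect on the proportions with a reduction cannot be sized from the documents, because the WPAI reduction definitions in SAP Table 1 are blacked out and no effect size is given.

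For the primary endpoint the consequence is a modest timing shift, with an upper end of about 7.0 to 7.4 months since first dose in the cases shown, against 6.5 if anchored to first dose.

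**What to change.** In SAP 5.1.1 and 5.1.4:

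- Take the initial fill date from the pharmacy data and tabulate days from first fill to Baseline and to the month-6 survey.
- Flag Baselines completed after first fill.
- Present the WPAI reduction and change analyses for Baselines completed before, or within a stated few days of, first fill, alongside the analysis of all patients. Fix the number of days in advance.
- Keep Baseline completion as the start of observation for event analyses, but label the results as time from Baseline. Report ER visits and hospitalizations between first fill and Baseline separately where dates allow.

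Cost: SAP wording, a few tables and one additional WPAI analysis. The fill date is only a proxy for the first dose. The restricted WPAI set will be smaller, most of all for the three work domains. The pharmacy transfer must also supply patient-level fill dates, and SAP 2.1 says that process has yet to be settled, so the requirement should be written into it now.
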